Appendix A: Deviations from SAP

This report below follows the statistical analysis plan version 1.0 dated 13/03/2023 apart from following:

Section of report not following SAP	Reason

Appendix B: Trial schema

Appendix C: Schedule of assessments

See trial protocol.

Appendix D: Data manipulations

The Trial Statistician will derive all responses from the raw data recorded in the database.

The following variables will be obtained directly from the raw data – where they are recorded in an appropriate form for analysis:

Cluster demographics

- Country (Kenya, Nigeria, South Africa, Tanzania)
- Number of births (total, caesarean, and vaginal) during study from weekly facility forms
- Number of births contributing to the study from pregnancy outcome forms
- Number of staff (Consultant Obstetrician; Medical Doctor; Clinical Officer; Medical Student; Nurse; Midwife; Nurse Midwife; Nurse/Midwifery student; other healthcare professional) – data is collected monthly, and the average number of staff in each category per month will be collated for each cluster

Individual patient demographics

- Previous births (Numerical)

- Previous caesarean section (Yes or No)
- PPH in previous pregnancy (Yes or No)
- Age (Numerical)
- Index birth
- Multiple pregnancy
- Mode of birth (Spontaneous vaginal or forceps or ventouse)
- Birth weight (Numerical)
- Gestational age at birth (Numerical)
- Antepartum haemorrhage (Yes or No)
- Preeclampsia (Yes or No)
- Labour augmented or induced (Yes or No)
- Retained placenta or manual removal of the placenta (Yes or No)

Primary Outcome Components

- Laparotomy for bleeding (Yes or No)
- Maternal mortality for bleeding (Yes or No)

Secondary/Exploratory Clinical Outcomes

- Laparotomy (Yes or No)
- Laparotomy with compression sutures (Yes or No)
- Laparotomy with arterial ligation (Yes or No)
- Hysterectomy (Yes or No)
- Hysterectomy for bleeding (Yes or No)
- All cause maternal mortality (Yes or No)
- All cause neonatal mortality (Yes or No)
- Non-pneumatic anti-shock garment (NASG) (Yes or No)
- Uterine balloon tamponade (Yes or No)
- Blood transfusion (Yes or No)
- Blood transfusion for bleeding (Yes or No)
- ICU admissions (Yes or No)
- Transfer to higher level cluster (Yes or No)

Secondary/Exploratory Implementation Outcomes

- PPH detection (Yes or No)
- Uterine massage (Yes or No)
- Oxytocin use (Yes or No)
- Misoprostol use (Yes or No)
- Tranexamic acid use (Yes or No)
- Intravenous fluids use (Yes or No)
- Examination of the genital tract (Yes or No)
- Women receiving any treatment uterotonic (Yes or No)
- Women requiring additional treatment interventions (Yes or No)

The following variables will be derived for analysis from the dataset. Details on how they will be derived is presented.

Cluster demographics

- Availability of bundle components – A daily facility diary denotes the availability of the bundle components (oxytocin, tranexamic acid, and IV fluid) for each cluster on each day of the study. The proportion of days in which each component is available will be calculated as a ratio of the number of days component was available and the total number of days. The proportion of days in which all components were available will be calculated as a ratio of the number of days with all components available and the total number of days.

Primary Outcome

- Primary outcome – The primary outcome is defined as being present if at least one of the three components are present (severe PPH, laparotomy for bleeding, maternal mortality for bleeding).

Primary Outcome Components

- Severe PPH – Severe PPH will be defined as present if the blood loss $\geq 1000\text{ml}$. The amount of blood loss for each participant will be determined from either:
 1. The weight of the drape (minus 130g which represents the dry weight of the drape for non-calibrated drapes, and minus 120g which represents the dry weight of the calibrated drapes)

[figure not shown]
Secondary/Exploratory Clinical Outcomes

- Primary PPH – defined as present if blood loss is $\geq 500\text{ml}$. The amount of blood loss is calculated as described above.
- Blood loss 2 hours postpartum - The amount of blood loss for each participant will be determined from either:
 1. The weight of the drape (minus 130g which represents the dry weight of the drape for non-calibrated drapes, and minus 120g which represents the dry weight of the calibrated drapes)
- Blood loss 24 hours postpartum – The amount of blood loss for each participant in the 24 hours will be calculated using the summation of:
 1. Blood loss 2 hours postpartum
 2. Additional blood loss in hours 2 to 24
- Duration of hospitalisation – Calculated as the difference between the date of giving birth and date of discharge.
- Duration of ICU hospitalisation – Calculated as the difference between date of admission to ICU and date of discharge to ICU.

[figure not shown]
Secondary Implementation Outcomes

- Compliance with MOTIVE bundle – Defined as adherence to three core elements of the bundle (oxytocic drugs, tranexamic acid, and IV fluid). Compliance is present if all three elements are present.

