4.5. Primary outcome measure

The primary outcome is a composite of the following three clinical outcomes:

- Primary severe PPH (defined as blood loss ≥ 1000 ml) following vaginal birth in the cluster measured up to 2 hours postpartum.
- Postpartum laparotomy for bleeding until discharge from the cluster.
- Postpartum maternal death from bleeding until discharge from the cluster.

If any of the components occur, this will be deemed as positive for the primary outcome.

The components of the composite primary outcome will be treated as secondary outcomes and examined individually as is recommended [3].

Measurement of blood loss

Blood loss will be collected using blood collection drapes for all women after vaginal birth. All facilities will use non-calibrated drapes during the baseline phase. During the intervention phase, clusters allocated to the control arm will continue to use non-calibrated drapes and clusters allocated to the intervention arm will use calibrated drapes containing measurement and trigger lines. The calibrated drapes are identical to the non-calibrated drapes with the only difference of having measurement and trigger lines to aid healthcare providers detect and treat PPH early. Blood loss will be measured for all women by weighing the blood collection drapes at the first hour postpartum, or if the bleeding continues, the blood collection will be extended to the second hour postpartum. The weight of the blood collection drape containing the blood will be recorded using digital weighing scales. If there is excessive, additional blood loss beyond the second hour postpartum up to 24 hours postpartum a visual estimation of blood loss will also be provided, and this will be included in the overall blood loss measurement as a secondary clinical outcome.

Only blood loss data that has been source verified will be included in the primary analysis – see below for details. Blood loss data that has not been source verified is included in a sensitivity analysis.

Source-verified data

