Analyses of outcomes with blood loss data will only include blood loss that has been source-verified. Blood loss measured using the blood collection drape, which is source-verified will have a corresponding photograph, which is uploaded to a secure portal, of the drape on the E-MOTIVE digital weighing scale displaying the drape weight. The photograph should also display the drape weight documented on the E-MOTIVE stickers before being placed in the patient notes. The drape weight value entered on to the E-MOTIVE REDCap database is verified against the drape weight in the photograph and the photograph is linked to the patient record on the database using the E-MOTIVE patient I.D number.

Blinded Endpoint Review Committee

A Blinded Endpoint Review Committee (BERC) will assess incoming data relevant to the primary outcome to confirm if any postpartum laparotomy was performed for bleeding and if any maternal death was due to bleeding. Initially, two central independent reviewers (identified by the TMG) will review de-identified data via the online E-MOTIVE database where there is a case of postpartum laparotomy and/or maternal death. The reviewers will not be able to view the facility's responses as to whether the postpartum laparotomy was for bleeding and/or the maternal death was due to bleeding. Each reviewer will be prompted to log in to the E-MOTIVE database and record their assessment on an electronic case report form (e-CRF) following receipt of an automated notification. If there is discordance between the assessments of the two reviewers or if their assessment conflicts with the assessment provided by the facility then a further assessment will be required by a central independent arbitration committee of five members convened by the TMG. The committee will meet as frequently as required and a decision will be made by a majority vote. The arbitration

committee will have access to the facility assessment (on the Discharge Outcome form) and the two independent reviewer assessments in order to make their decision. The Programme Manager (or delegate) will minute committee discussions and enter a summary of the discussions along with their decision on to the e-CRF. The review by the BERC members will be undertaken blinded to the randomised allocation of the health facility. Members of the BERC are required to formally register their assent to join the committee by signing a separate charter. Further details of the BERC can be found in their charter.

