4.6. Secondary clinical and implementation outcome measures

Key Implementation Outcomes

The key implementation outcomes are:

- 1) Postpartum haemorrhage detection
- 2) Compliance with the MOTIVE bundle

These are defined below.

Postpartum haemorrhage detection

Postpartum haemorrhage (PPH) detection has the following numerator and denominator: women who objectively had PPH (source verified blood loss ≥ 500 mL after weighing the drape) and were diagnosed with PPH by the birth attendants divided by the total number of women who objectively had PPH (source verified blood loss ≥ 500 mL after weighing the drape).

Compliance with the MOTIVE bundle

Compliance with the MOTIVE bundle has the following numerator and denominator: women who objectively had PPH and were treated with the PPH bundle following a diagnosis of PPH by the birth attendants divided by the total number of women who objectively had PPH (blood loss ≥ 500 mL after weighing of the drape). Compliance with the MOTIVE bundle is defined as adherence to the three core elements of the bundle: administration of oxytocic drugs, TXA and IV fluids. If all three core elements are administered when a PPH is diagnosed, this will be deemed positive for bundle compliance. If any of the three core elements are not administered when a PPH is diagnosed, then this will be deemed negative for bundle compliance.

Secondary Clinical Outcomes

The secondary clinical outcomes are based on the Core Outcome Set for PPH treatment, and are the following:

1. Laparotomy postpartum until discharge from the cluster*;
2. Laparotomy with compression sutures postpartum until discharge from the cluster*;
3. Laparotomy with arterial ligation postpartum until discharge from the cluster*;
4. Hysterectomy postpartum until discharge from the cluster*;
5. Hysterectomy postpartum for bleeding until discharge from the cluster*;
6. All-cause maternal mortality postpartum until discharge from the cluster*;
7. Blood loss (reported in ml) up to 24 hours postpartum†;

8. Primary PPH defined as blood loss ≥ 500 ml up to 24 hours postpartum[†];
9. Duration of hospitalisation postpartum;
10. Duration of ICU hospitalisation postpartum until discharge from the cluster[†];
11. Transfers to higher-level facility postpartum until discharge from the cluster;
12. All-cause neonatal mortality postpartum until discharge from the cluster*;
13. Use of Non-pneumatic anti-shock garment (NASG) postpartum[†];

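### SAP Appendix D derives primary PPH, defined up to 24 hours, from the drape weight, which covers at most the first 2 hours

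*SAP*

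**What the plan says.** **Definition.** SAP 4.6, item 8: "Primary PPH defined as blood loss ≥ 500 ml up to 24 hours postpartum". Protocol 6.2, item 8, has the same threshold and window.

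**Derivation.** SAP 7.5 sends the analyst to Appendix D. For primary PPH, Appendix D repeats the 500 ml threshold, gives no window, and adds "The amount of blood loss is calculated as described above". The method above it, under severe PPH, begins "The weight of the drape (minus 130g which represents the dry weight of the drape for non-calibrated drapes" and continues with 120 g for calibrated drapes. Below the primary PPH line, Appendix D defines 2-hour blood loss (drape) and 24-hour blood loss (the 2-hour value plus additional loss in hours 2 to 24).

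**What the drape covers.** SAP 4.5 has the drape weighed at the first hour, and "if the bleeding continues, the blood collection will be extended to the second hour postpartum". The severe PPH component is worded to match: "Primary severe PPH (defined as blood loss ≥ 1000 ml) following vaginal birth in the cluster measured up to 2 hours postpartum".

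**Loss after 2 hours.** If later loss is excessive, SAP 4.5 says "a visual estimation of blood loss will also be provided, and this will be included in the overall blood loss measurement". The section places this total among the secondary clinical outcomes.

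**Source verification.** SAP 4.5, under measurement of blood loss, limits the primary analysis to verified blood loss. Under source-verified data it says more broadly: "Analyses of outcomes with blood loss data will only include blood loss that has been source-verified". Protocol 6.1 and 11.2 contain the same pair of statements. Verification is described only as a photograph of the drape on the scale, checked against the entered weight.

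**The concern.** Section 4.6 and Appendix D give two different variables for one named outcome, and Appendix D is the text from which the outcome will be programmed. An analyst who follows it produces a 2-hour variable. A reader of the report who looks up the definition will take it for a 24-hour one.

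The results table does not settle the matter. In Appendix E5 the continuous blood-loss rows are labelled 2 hours and 24 hours, but the primary PPH row carries only the 500 ml threshold. Under Appendix D, primary PPH would also rest on the same weighed-drape criterion that identifies women who objectively had PPH for the key implementation outcomes. The information from hours 2 to 24 would then not enter it at all.

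The broad verification sentence adds a smaller uncertainty. Read on its own, it would remove the visual estimate from the 24-hour outcomes that the same section says should include it.

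**Working it through.** The plan states no figure on this point, so the check is a comparison of texts.

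| Item | Threshold | Window | Blood loss used |
|---|---|---|---|
| Protocol 6.2 and SAP 4.6, item 8 (primary PPH) | 500 ml | 24 hours | not specified |
| Appendix D, severe PPH | 1000 ml | 2 hours (from SAP 4.5) | drape minus dry weight |
| Appendix D, primary PPH | 500 ml | none given | refers back to the row above |
| Appendix D, 24-hour blood loss | continuous | 24 hours | 2-hour loss plus loss in hours 2 to 24 |

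1. Let D be the weighed drape loss and V the visual estimate for hours 2 to 24, with V not negative.
2. SAP 4.6 counts a woman as having primary PPH if D + V ≥ 500 ml. Appendix D counts her if D ≥ 500 ml.
3. The two rules disagree exactly when D < 500 ≤ D + V. The disagreement runs one way only: Appendix D can miss cases under the 24-hour definition but cannot add any.
4. Illustration with assumed values: D = 450 ml and V = 200 ml give 450 + 200 = 650 ml. That is primary PPH under SAP 4.6 and not under Appendix D.
5. Effect on the crude risk ratio: let p1 and p0 be the proportions with D ≥ 500 ml in the two arms, and l1 and l0 the proportions who cross only later. The 2-hour ratio is p1/p0 and the 24-hour ratio is (p1 + l1)/(p0 + l0). They are equal when l1/p1 = l0/p0 and differ otherwise. The documents give none of these four quantities.

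**Reach.** The severe PPH component of the primary composite has a 2-hour window. Both key implementation outcomes use blood loss from the weighed drape, and the baseline PPH-rate subgroup in SAP 7.10 is expressly drape-based. The power calculation concerns the composite. None of these depends on V. The outcomes that do are secondary clinical outcomes 7 (24-hour blood loss) and 8 (primary PPH).

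**The case against.** **The text may be incomplete.** In Appendix D the severe PPH method is introduced as a choice between alternatives, but one item follows, and a figure is missing just after it. An item may have been lost in reading the PDF. This lowers certainty about the full wording, but it is unlikely to remove the conflict: the method serves a 2-hour outcome, and the 24-hour sum is defined separately, below primary PPH.

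**The outcome carries little weight.** Primary PPH is one of 20 secondary clinical outcomes and is marked as one that could move either way if the intervention works. It has no planned p-value and is supporting evidence only (SAP 5.1). This stands, and it limits the consequence. It does not make the two definitions agree.

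**The verification rule.** A reader might infer that the 24-hour outcomes cannot satisfy the verified-only rule and so cannot be analysed as planned. The documents do not support that. SAP 4.5 and Protocol 6.1 expressly include the visual estimate in a secondary outcome, and the next statement on verification is confined to the primary analysis. Appendix D then adds the later loss in. The broad sentence is followed at once by a description that concerns only drape measurements. The intention is reasonably clear, and what is needed is a clarifying clause.

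**Conclusion.** The mismatch of windows is real. Appendix D is wrong as written for primary PPH, because it states a rule that contradicts SAP 4.6 and Protocol 6.2. Women who reach 500 ml only in hours 2 to 24 would be classified as not having PPH.

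The size cannot be computed, because the documents give no frequency of late crossing. A reader might try to infer one from an assumed blood-loss distribution. The plan does not support that: it gives no distribution or median, its 3.6% is the prevalence of the composite rather than of blood loss of at least 1000 ml, and its 4% is a power scenario. Any such figure would also describe a shift in the PPH rate. Whether the risk ratio moves depends on how late crossing compares between arms, and the documents give no figure for that.

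Nor should the point be read as touching the trial's main conclusion. It is confined to secondary clinical outcomes 7 and 8, with outcome 7 affected only through the verification wording. The conclusion assumes that no lost Appendix D text redefines primary PPH over 24 hours. The correction should be made, and it is small.

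**What to change.** 1. In Appendix D, derive primary PPH from the 24-hour blood-loss variable already defined there, so that it matches SAP 4.6 and Protocol 6.2. If the drape-only version is what is intended, relabel item 8 as a 2-hour outcome in SAP 4.6 and in the Appendix E5 table, and align Protocol 6.2.
2. Put the chosen window in the primary PPH row or footnote of Appendix E5.
3. Add one clause to the source-verified data text in SAP 4.5 and Protocol 11.2: verification applies to the drape component, and the visual estimate for hours 2 to 24 is included in the 24-hour secondary outcomes, as SAP 4.5 already provides.
4. Optional: report a weighed-only, 2-hour version of primary PPH beside the 24-hour one, labelled as such.

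The cost is a few lines of wording, plus one table row if the optional version is reported. No new data are needed, since Appendix D already defines both blood-loss variables. If the analysis has already been run, state which derivation was used; any departure from the SAP text belongs in the Appendix A deviations table.

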Appendix E1: CONSORT flow diagram

Appendix E2: Timeline Cluster Graphical Tool Example

1	Cluster (Health Facility) identification
2	Cluster recruitment
3	Patient identification
4	Outcome assessment – baseline period
5	Randomisation
6a	Intervention delivery
6b	Usual care
7	Outcome assessment – post-randomisation period

Appendix E3: Baseline characteristics

Health facility level characteristics	E-MOTIVE		Control	
	Baseline period (N =)	Post-randomisation period (N =)	Baseline period (N =)	Post-randomisation period (N =)
Facility location				
Country				
Kenya				
Tanzania				
Nigeria				
South Africa				
Facility demographics				
Total number of births per facility ²				
Mean (SD)/Median [IQR]				
Number of vaginal births per facility ³				
Mean (SD)/Median [IQR]				
Number of caesarean sections per facility ⁴				
Mean (SD)/Median [IQR]				
Number of skilled birth attendants				
Mean (SD)/Median [IQR]				

Availability of bundle
components ⁶
(months/proportion/??)

Mean (SD)/Median [IQR]

Patient demographics	E-MOTIVE		Control	
	Baseline period (N =)	Post-randomisation period (N =)	Baseline period (N =)	Post-randomisation period (N =)
Previous birth information				
Previous births				
0				
1				
2				
3				
4				
5 or greater				
Mean (SD)/Median [IQR]				
Missing				
Previous caesarean section				
Missing				
PPH in previous pregnancy				
Missing				
Age (years)				
Mean (SD)/Median [IQR]				
Range				
Missing				
Index birth				
Multiple pregnancy				
Singleton				
Multiple pregnancies				
Missing				
Mode of birth				
Spontaneous birth				
Instrumental births				
Missing				

Birth weight (g)	Mean (SD)/Median [IQR]
	Range
	Missing
Gestational age at birth (weeks)	Mean (SD)/Median [IQR]
	Range
	Missing
Gestational age <37 weeks	Missing
Antepartum haemorrhage ¹	Missing
Preeclampsia ²	Missing
Labour augmented or induced	Missing
Retained placenta or manual removal of the placenta ³	Missing

Appendix E4: Primary outcome results

Table 3: Main outcomes. Values are number (percentage) unless otherwise stated.

Outcomes	E-MOTIVE		Control		Risk Ratio (95% CI)	p-value	Risk Difference (95% CI)*	p-value
	Baseline period (N =)	Post-randomisation (N =)	Baseline period (N =)	Post-randomisation period (N =)				
Primary Outcome								
Primary Outcome ²								
Key Implementation Outcomes								
PPH detection ³						-	-	
Compliance with MOTIVE bundle ⁴						-	-	

PPH: Post partum haemorrhage. ICU: Intensive care unit.

* Differences between risks are presented in percentage points, and differences between mean values are presented in the unit of the mean values

1: Adjusted for the period in which the observation was made and cluster-level covariates used in the randomisation (number of vaginal births, PPH rate, country, and the primary outcome rate)

2: Primary outcome was a composite of: severe postpartum hemorrhage (blood loss \geq 1000ml); laporotomy for bleeding; and maternal mortality from bleeding.

3: Defined as recording of diagnosis of PPH by birth attendant.

4: Defined as adherence with three core elements of the bundle: administration of oxytocic drugs, TXA, and IV fluids.

Appendix E5: Secondary outcomes results

Table 4: Main outcomes. Values are number (percentage) unless otherwise stated.

Outcomes	E-MOTIVE		Control		Risk Ratio ¹ (95% CI)	Risk Difference ¹ (95% CI)*
	Baseline period (N =)	Post-randomisation period (N =)	Baseline period (N =)	Post-randomisation period (N =)		
Secondary Clinical Outcomes						
Severe PPH ²						
Laparotomy for bleeding						
Maternal mortality from bleeding						
Primary PPH ³						
Laparotomy						
Laparotomy with compression sutures						
Laparotomy with arterial ligation						
Hysterectomy						
Hysterectomy for bleeding						
All cause maternal mortality						
All cause neonatal mortality						
Non-pneumatic anti-shock garment (NASG)						
Uterine balloon tamponade						
Blood transfusion						
Blood transfusion for bleeding						
ICU admissions						
Transfer to higher level facility						

	E-MOTIVE				Control		Mean difference ¹ (95% CI)*	
	Baseline period (N =)	Post-randomisation period (N =)	Baseline period (N =)	Post-randomisation period (N =)				
Blood loss 2 hours postpartum (ml), mean (SD)						-		
Blood loss 24 hours postpartum (ml), mean (SD)						-		
Duration of hospitalisation (hours), mean (SD)						-		
Duration of ICU hospitalisation (hours), mean (SD)						-		
Other Secondary Implementation Outcomes	E-MOTIVE		Control		Risk Ratio ¹ (95% CI)		Risk Difference ¹ (95% CI)*	
In women with ≥500ml blood loss	Baseline period (N =)	Post-randomisation period (N =)	Baseline period (N =)	Post-randomisation period (N =)				
Uterine massage								
Oxytocin use								
Misoprostol use								
Tranexamic acid use								
Intravenous fluids use								
Examination of the genital tract								
Women receiving any treatment uterotonic								
Women requiring additional treatment interventions								
In women diagnosed with PPH by HCP⁴								
Bundle compliance ⁵								
Uterine massage								
Oxytocin use								

Misoprostol use
 
Tranexamic acid use
 
Intravenous fluids use
 
Examination of the genital tract
 
Women receiving any treatment uterotonic
 
Women requiring additional treatment interventions
 
In all women
 
Detection of PPH by HCP ⁴
 
Bundle compliance ⁵
 
Uterine massage
 
Oxytocin use
 
Misoprostol use
 
Tranexamic acid use
 
Intravenous fluids use
 
Examination of the genital tract
 
Women receiving any treatment uterotonic
 
Women requiring additional treatment interventions
		
---	--	--

PPH: Post partum haemorrhage. ICU: Intensive care unit.

* Differences between risks are presented in percentage points, and differences between mean values are presented in the unit of the mean values

1: Adjusted for the period in which the observation was made and cluster-level covariates used in the randomisation (number of vaginal births, country, and the primary outcome rate)

2: Defined as blood loss $\geq 1000\text{ml}$.

3: Defined as blood loss $\geq 500\text{ml}$.

4: Defined as recording of diagnosis of PPH by birth attendant.

5: Defined as adherence with three core elements of the bundle: administration of oxytocic drugs, TXA, and IV fluids.

